4 STUDY POPULATION PARAMETERS

4.1 DISPOSITION

VTI-308 End of Study Disposition and VTL-308E Disposition at time of cut-off of all subjects will be presented in a table by treatment group for ITT population. These presentations will include the number of subjects who completed their Study Day 91 visit and the number who discontinued, as well as the reason for study discontinuation. The disposition for subjects who entered VTL-308E when the database locks will also be provided. Survival status at time of Day 91, Day 180, Day 365 and time of cut-off will be summarized using ITT populations. Additionally, subjects who received a liver transplant and/or were diagnosed with cancer will be summarized using the ITT population.

4.2 PROTOCOL DEVIATIONS

Protocol deviations will be divided into two distinct groups.

- Major deviations will include:
 - Subjects who were randomized but had failed to meet all of the inclusion criteria or have at least one of the exclusion criterion;
 - Subjects who incorrectly received a treatment regimen that differs from the treatment specified by the randomization schema;
 - Subjects in whom
 - treatment was initiated with ELAD C3A cell cartridges that started recirculation (centrifugal pump start at 2LPM) in the ELAD System more than 60 hours after being removed from the bioreactor;
 - treatment was carried out with more than two different sets of cell cartridges.
- All deviations not categorized as major will be deemed minor.

All protocol deviations will be reviewed by the medical monitor, and/or a member of the clinical operations team to verify that the major and minor protocol deviation classifications are correct.

4.3 STANDARD OF CARE COMPLIANCE

Compliance to the Standards of Care (SOC) will be assessed for each subject after Randomization up to Study Day 91.

A method will be developed and employed to assess compliance with all categories of SOC. The specific questions that will be asked in order to determine compliance with each SOC are provided in [Appendix A](#). These data will be used to determine whether there is a difference in SOC between treatment groups and to conduct further analyses on SOC compliance.

Subject compliance with SOC will be established by first determining whether or not the subject should have received the SOC (i.e. had the condition requiring the SOC to be administered). If a subject has the condition and is appropriately administered SOC, the subject will be considered to be compliant. If a subject does not have the condition and is not administered the SOC, the subject will also be considered to be compliant. If a subject has the condition and is not administered SOC, the subject will be considered non-compliant with that SOC. The proportion of subjects who were compliant will be assessed by dividing the number of subjects considered

compliant with each SOC (whether or not they have the condition requiring that SOC) by the total number of subjects in each SOC for each treatment group.

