7.3 PRIMARY EFFICACY ANALYSIS

7.3.1 Overall Survival (OS) of AILD Subjects through at Least Study Day 91

OS will be assessed using a Kaplan-Meier survival analysis of the intent-to-treat (ITT) population utilizing a log-rank test, with follow-up Protocol VTL-308E providing additional survival data up to a maximum of 5 years that will be included, as available, through VTL-308

study termination. Model-based estimates and confidence limits will be calculated for median survival by treatment group and the hazard ratio and its confidence limits. This analysis will also be carried out on the mITT, Per-Protocol (PP) and Safety populations as sensitivity analyses. Two-tailed alpha for the log-rank test will be set at 0.05. The statistical analysis plan will outline the methods used to account for missing data in this and all other analyses.

The statistical analysis plan will also evaluate differences in standard of care between the groups that may affect subject outcome, such as differences in the administration of steroid therapy, and define analytical strategies to deal with those differences should they arise.

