1.3 SAMPLE SIZE RATIONALE

The sample size is based on experience from the VTI-208 study.

The VTL-308 inclusion criteria have been established to reflect a subset of the VTI-208 population, i.e. the VTI-208 population with baseline criteria of MELD <30, age <50, INR \leq 2.5, creatinine <1.3 mg/dL and serum total bilirubin \geq 16 mg/dL.

The key design feature of the VTL-308 Protocol is that the primary analysis of treatment effect on overall survival is based on a log-rank statistic having two-sided significance level of 0.05. This primary analysis will be performed when the last of 150 randomized subjects has been followed for at least 91 days. Sample size adjustments may be made only in the instance in which more than 150 randomized subjects would be needed in order to achieve the minimum threshold of 55 deaths at the time of that analysis.

When the study is nearing completion of enrollment, the total number of deaths occurring through that time will be calculated, along with the mortality rate, based on the enrollment rate per month and the time to death. Based on these calculations a projection will be made of the total number of subjects that will need to be enrolled to achieve the minimum threshold of 55 deaths at the time of study data lock (estimated to be approximately 5 months after last patient enrolled). The total sample size may then be adjusted accordingly.

Analysis of the VTI-208 data suggests that in a group of subjects meeting the inclusion criteria for VTL-308, it might be reasonably anticipated that one-year survival will be in the range from 40% to 48% in the Control group. Under the assumption of a proportional hazards model, if the hazard ratio is 0.4 in favor of the ELAD group, this leads to the anticipation that one-year survival will be in the range from 69.5% to 74.5% in the ELAD subjects.

The rationale for the sample size is based on the following assumptions:

- the analysis of the primary endpoint of overall survival will be conducted in the ITT population;
- the prospectively defined population behaves similarly to the corresponding subgroup of the VTI-208 study;
- the log-rank test will be used to compare two survival curves using a two-sided significance level of 0.05;
- one-year survival will be in the range from 40% to 48% in the Control group and in the range from 69.5% to 74.5% in the ELAD group;
- the accrual distribution will be uniform with an accrual time that will be at least 720 days;

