- the rate of missing data will be in the range from 0% to 10%; and
- the primary analysis will be the time when at least 55 deaths have occurred and the time when the last enrolled subject has been followed for at least 91 days. It follows that a sample size for the VTL-308 trial of 75 subjects per group with 1:1 allocation would provide a number of events (i.e., deaths) in the range from 55 to 65, even if we assume average follow-up of only 1 year. With 55 events, the trial will have 90% power if the true hazard ratio is 0.417; with 65 events, the trial will have 90% power if the true hazard ratio is 0.447.

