7.1.4 Assessment of Potential Bias due to Treatment Group Assignment

VTL-308 is an open-label study. While every effort has been made in the study protocol to minimize the effects of post-treatment differences in investigator evaluation, medical care and subject behavior, there is a potential that differences in these factors may be associated with treatment group assignment, and that these differences might influence outcomes. An evaluation of the proportion of survivors at Study Days 28 and 91 will be carried out to determine whether these differences had any impact on study outcome. Parameters assessed will include, but not be limited to, the following:

- Alcohol use post-discharge. This will be evaluated based on either a PEth result of >20 ng/mL (evidence of moderate or heavy alcohol consumption) or any self-report of alcohol use post-discharge (note: a positive PEth result will supersede a self-report of no alcohol use);
- Length of Initial ICU Stay (<Median and ≥Median), defined as the first ICU discharge date minus ICU admission date plus 1, if the admission date is after randomization. If the admission date is before randomization, then the length of stay will be the discharge date minus randomization date plus 1. If the discharge date is missing and the subject died, the death date will be used;
- Length of Initial Hospital Stay (<Median and ≥Median), defined as the hospital discharge date minus randomization date plus 1. If discharge date is missing and the subject died, the death date will be used;
- Steroids Use Post-randomization (Yes/No);
- Steroids Use Post-randomization for <7 days (Yes/No);

- Steroids Use Post-randomization for ≥ 7 to < 14 days (Yes/No);
- Steroids Use Post-randomization for ≥ 14 to < 28 days (Yes/No);
- Steroids Use Post-randomization for at least 28 days (Yes/No);
- Concomitant heparin use within the first 10 days of the study (Yes/No);
- For the ELAD group only, ELAD treatment duration dichotomized based on < 72 hours vs. ≥ 72 hours. This analysis will be based on total ELAD treatment duration inclusive of any time off treatment (i.e., final stop date/time of treatment, defined as the time at which the ultrafiltrate pump is switched off for the last time – initial start date/time of treatment, defined as the time at which the ultrafiltrate pump is switched on for the first time). Additional analyses of ELAD treatment duration are described in [Section 8.2](#) and [8.10.1](#).

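### SAP 4.3 counts subjects who never needed a standard of care as compliant, so the table dilutes care differences for uncommon conditions and mixes care with condition incidence

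*SAP*

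**What the plan says.** SAP 4.3 assesses compliance for each subject from randomization to Study Day 91. It first asks whether the subject "had the condition requiring the SOC to be administered". A subject with the condition who was treated appropriately is compliant, and one with the condition who was not treated is non-compliant. For the rest, "If a subject does not have the condition and is not administered the SOC, the subject will also be considered to be compliant". The proportion takes subjects "compliant with each SOC (whether or not they have the condition requiring that SOC) by the total number of subjects in each SOC", by treatment group. On use, the section says: "These data will be used to determine whether there is a difference in SOC between treatment groups". It names no test, significance level or threshold.

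Protocol 7.3.1 commits the SAP to "evaluate differences in standard of care between the groups that may affect subject outcome", giving steroid therapy as its example, and to define how such differences would be handled. SAP 7.1.4 begins from the fact that "VTL-308 is an open-label study" and accepts that medical care may differ by assigned arm and may influence outcome.

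SAP Appendix A lists the questions behind each assessment. Seven of its nine categories are triggered by a condition: ascites, gastroesophageal varices, hepatic encephalopathy, hepatorenal syndrome (HRS), hyponatremia, spontaneous bacterial peritonitis (SBP) and hepatic hydrothorax. The other two are nutrition and steroids.

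**The concern.** Whether care differed between arms is a question about subjects who needed the care. The SAP 4.3 proportion answers a different question, because it combines how often the condition occurred with how well it was treated. A subject who never had HRS adds one compliant case to the HRS row and says nothing about how HRS was managed.

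Two consequences follow. For an uncommon condition, both arms can show high percentages even when those who needed care were treated quite differently. And because status is assessed to Day 91, the frequency of a condition can itself depend on the assigned treatment, so a gap in the table may reflect incidence and not care.

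What is at stake is the strength of the reassurance. Treating staff know the assignment, and the Protocol promises that care differences will be evaluated.

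**Working it through.** The documents give no compliance or prevalence figure, so there is no stated number to reproduce.

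**Inputs.** The classification rule and denominator come from SAP 4.3. Arm size comes from SAP 1.3 ("75 subjects per group with 1:1 allocation"). Prevalence q and compliance c among subjects with the condition are assumptions. The two-sided 0.05 level is borrowed from the primary test, since SAP 4.3 sets none.

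**Formula.** Displayed compliance in an arm is A = (1 − q) + q·c = 1 − q(1 − c). The formula assumes that nobody without the condition receives the SOC, because SAP 4.3 does not classify that group. The phrase for the denominator is not fully clear. It is read as all subjects in the arm because, if it meant only subjects with the condition, the proportion could exceed 100%.

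**Equal prevalence.** The displayed difference is q × (true difference).

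| q | True compliance | Displayed | True gap | Displayed gap |
|---|---|---|---|---|
| 10% | 90% vs 50% | 99% vs 95% | 40 | 4 |
| 20% | 90% vs 50% | 98% vs 90% | 40 | 8 |
| 20% | 90% vs 60% | 98% vs 92% | 30 | 6 |
| 50% | 90% vs 60% | 95% vs 80% | 30 | 15 |
| 100% | 90% vs 60% | 90% vs 60% | 30 | 30 |

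For example, at q = 20%: 1 − 0.2 × 0.1 = 98% and 1 − 0.2 × 0.5 = 90%.

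**Unequal prevalence (ELAD vs Control).** The direction is no longer fixed.

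- A difference is created. Care is 80% in both arms, q = 40% vs 20%: 1 − 0.4 × 0.2 = 92% vs 1 − 0.2 × 0.2 = 96%.
- A difference is hidden. Care is 70% vs 90%, q = 20% vs 60%: 1 − 0.2 × 0.3 = 94% vs 1 − 0.6 × 0.1 = 94%. A true 20-point gap disappears.
- A difference is enlarged. Care is 85% vs 90%, q = 60% vs 20%: 1 − 0.6 × 0.15 = 91% vs 1 − 0.2 × 0.1 = 98%. A true 5-point gap shows as 7.

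**Power, 75 per arm.** At q = 20% about 15 subjects per arm have the condition (75 × 0.2).

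| True contrast at q = 20% | Method | Condition only | SAP rule |
|---|---|---|---|
| 90% vs 50% | Normal approximation | 68% | 54% |
| 90% vs 50% | Fisher's exact test | 54% | 40% |
| 90% vs 60% | Normal approximation | 47% | 39% |

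The approximation is rough with 15 per arm. At q = 10% (7 or 8 per arm) condition-only Fisher power for 90% vs 50% is only about 13% to 22%. The loss of power is therefore smaller than the loss of apparent effect size, and restricting the denominator does not make a rare condition informative.

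**The case against.** **The rule does not bias everything, or in one direction.** A reader might infer that it shrinks every care difference towards zero. It does not. Protocol 5.4.1.1 gives a dietary consult to all subjects and Protocol 5.4.1.2 gives steroids to all unless contraindicated, so the consult is not diluted and steroids are diluted only through contraindications. Steroids are also the one example that Protocol 7.3.1 names. With unequal incidence the distortion can go either way. This objection stands, and it limits the point to condition-triggered items.

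**Compliance would not read near 100% whatever was done.** At 20% prevalence, complete failure to treat would display as 80%. This also stands. The table is blunted, not blind.

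**Care is examined elsewhere.** SAP 7.1.4 relates steroid use and duration, heparin, and ICU and hospital stay to survival. SAP 8.4 and 8.7 summarize medications, blood products and procedures by arm, and SAP 8.10 lists reasons why steroids were not started. SAP 4.3 itself allows further compliance analyses, and Appendix A lists the condition and treatment questions from which a restricted rate could be built. So SAP 4.3 is not the only look at care. But none of the other planned analyses is restricted to subjects who needed the care, and no such rate is specified.

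**Restricting to subjects with the condition has its own problem.** For conditions that arise after randomization, it selects on an event that treatment may affect, so the comparison is not protected by randomization. This is correct, and it is why the restricted table should be labelled descriptive. The all-subject rate does not avoid the problem, because differing incidence enters that rate unseen.

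**Conclusion.** The point holds for condition-triggered SOCs and for the conditional nutrition items (malnutrition, metal and vitamin deficiencies). With similar prevalence in the arms, the SAP 4.3 proportion shows only the fraction q of a true care difference: one fifth at 20% prevalence and one tenth at 10%. With differing prevalence it can hide, create or enlarge a difference. The algebra follows from the SAP's rule, but every numerical example rests on assumed prevalence and compliance.

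A reader might go further and conclude that the survival result is compromised. The documents do not support that: the proportion enters neither the primary log-rank test nor any secondary efficacy analysis. The consequence is a weak check on equal care in an open-label trial. It should be corrected because the table is meant to answer that question and the correction is cheap.

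**What to change.** Amend SAP 4.3 and its table shell as follows.

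- For each condition-triggered SOC, and for each conditional nutrition item, report by arm the number with the condition, the number compliant among them, and the percent, with a confidence interval for the between-arm difference.
- Identify these subjects from all the relevant Appendix A questions, since the first question under each heading is not always enough. Hyponatremia has separate hypovolemic and hypervolemic questions. SBP has a current-episode and a prior-episode question. HRS needs Type I separated, because that is the only type whose treatment Appendix A assesses.
- Show subjects for whom the SOC was not indicated in their own row, and state how a subject without the condition who received the SOC is classified.
- Keep all subjects as the denominator for the dietary consult and, apart from contraindications, for steroids. Elsewhere, keep the all-subject rate only as a supplement.
- Label the comparison descriptive, because it conditions on events that can occur after randomization.

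Appendix A already asks for the inputs, so no new data items are needed. The cost is a few sentences in the SAP and a changed table. Reported percentages will be lower, and intervals for rare conditions will be wide.

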4.4 DEMOGRAPHIC AND BASELINE CHARACTERISTICS

Baseline comparability of the treatment groups will be assessed with respect to demographic variables, screening vital signs, and medical history. Summary statistics (N, mean, standard deviation (SD), median, minimum, maximum and proportions, as appropriate) will be presented by treatment group for the ITT population. If more than one screening value is recorded, the last record before the randomization date will be used for analysis.

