5.2.3 Screening Procedures

The tests and assessments listed below must be performed prior to Randomization, unless otherwise noted (see [Section 5.2.3.2](#) regarding imaging requirements). An overview of these procedures is presented in [Table 1](#) of this protocol.

Procedures that are performed one time as part of the Screening process are as follows:

- Demographics (date of birth or age, race, ethnicity, height, weight, gender)
- Relevant medical history
- Documented evidence of temporal association (6 weeks or less) of alcohol use and hospital admission for this episode of AILD. Documented evidence includes patient or other credible person reporting alcohol use, and/or positive blood test
- Liver imaging to determine liver size and confirm the absence of occlusive portal vein thrombosis or bile duct obstruction (see [Section 5.2.3.2](#) regarding imaging performed no more than six weeks prior to current hospitalization)
- Serologies (if not previously collected during this hospitalization, and investigator suspects subject may be at risk) for active viral hepatitis A, B or C infection or human immunodeficiency virus (HIV); a positive serology for active hepatitis would be exclusionary
- Serum pregnancy test⁺⁺ (if applicable)

⁺⁺ Note: Subjects who are sexually active, without history of medical or surgical sterilization, must agree to practice a form of effective contraception. Instruction should be given that if a subject becomes pregnant or impregnates another during participation in the study, they must inform the Principal Investigator immediately. Female subjects that become pregnant and report this to the Principal Investigator will be followed through to the completion of the pregnancy, including delivery and status of the neonate. The partner of a male ELAD-treated subject who is impregnated during the time between Randomization to Study Day 91 will not be followed.

Procedures that are performed as part of the Screening process and which are used as Baseline values required for subsequent assessments of change in key parameters are as follows (Note: these tests and assessments must be performed within 24 hours prior to randomization):

- Physical exam (performed by a Physician, Physician Assistant or Nurse Practitioner if within the scope of practice for institution)
- Vital signs (blood pressure, heart rate, respiration rate, temperature)

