4.4.2 Severe Alcoholic Hepatitis

Baseline sAH characteristics to be summarized for the ITT population include:

- Steroids >6 weeks prior to baseline (Yes/No); response to steroid treatment (Yes/No/Unknown);
- Steroids during the 6 weeks prior to baseline (Yes/No); response to steroid treatment (Yes/No); and method used to assess response;
- Selected medical treatments at baseline (steroids, pentoxifylline, N-acetyl-cysteine);
- MELD score with corresponding components (creatinine, total bilirubin, and INR);
- Maddrey score with corresponding components (prothrombin time [PT], laboratory control PT, and total bilirubin);
- Subjects that had dialysis at least twice in the past week
- Time from last alcohol consumption to hospital admission (weeks); and
- Time from hospital admission to Randomization (days).

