7.3.6 Selected Labs and MELD Scores Summarized by Visit

Changes in selected lab values and disease severity scores that have been demonstrated to correlate with survival will be presented for the ITT population. Differences between treatment groups at each time point will be analyzed based on a mixed model repeated measure (MMRM) with fixed effects of treatment group, visit and the treatment group by visit interaction, and a covariate of baseline value for the corresponding treatment. An unstructured covariance matrix will be used. If the model does not converge with an unstructured covariance matrix due to insufficient data at some visits, the spatial power covariance structure will be used. In addition, one sample t-test will be used to test if change from baseline value is zero at each time point within treatment group. All changes will be calculated relative to randomization date/time (as all subjects are on standard of care treatment as of the randomization date/time). Additional summaries of changes relative to ELAD start date/time will be provided for selected analyses. For comparative purpose, the Control group will be summarized by changes relative to End of Study Day 2, as this most closely mimics the time of initiation of ELAD treatment in those subjects randomized to ELAD. If Study Day 2 is missing for Control subjects, the last non-missing visit before Study Day 2 will be used for analysis.

As a sensitivity analysis, the analyses will be repeated after the missing data is imputed using the last observation carried forward (LOCF) approach. These will include:

- MELD;
- Total Bilirubin;
- Creatinine;
- INR;
- Sodium.

The values for MELD, Total Bilirubin, Creatinine, INR and Sodium will be displayed in a listing.

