8.5 CHEMISTRY, HEMATOLOGY, COAGULATION, DISEASE-SPECIFIC EVALUATIONS

Data will be summarized by treatment group based on means by study visit, and mean (both absolute and %) changes from baseline by study visit. The baseline evaluation of a laboratory parameter is defined as the last evaluation of that parameter prior to randomization date/time. Additional summaries of changes relative to ELAD start date/time will be provided for subjects in the ELAD treatment group. For comparison purpose, changes relative to End of Study Day 2 will be summarized for the Control treatment group. Laboratory data will be prioritized over MELD/Maddrey data, if more than one measurement is recorded on the same study day.

For the following lab tests, proportion of subjects meeting the specified criteria will be presented by treatment group at each study visit:

- Bilirubin: <12 mg/dL vs. ≥12 mg/dL;
- Bilirubin: <16 mg/dL vs. ≥16 mg/dL;
- Hemoglobin: <7 g/dL;
- Platelet count: ≤20,000/mL;
- INR: >2.5 and >3.5;
- Calcium: ≤0.88 mmol/L;
- Glucose: >350 mg/dL or <50 mg/dL;
- Lactate: >4 mmol/L;
- Magnesium: <1.0 mEq/L;
- Phosphorus: <0.3 mmol/L;
- Potassium: >7.0 mEq/L or <2.0 mEq/L;
- Creatinine: Change <0.3 mg/dL vs. Change ≥0.3 mg/dL;
- Sodium: <130 mEq/L vs. ≥130 mEq/L;
- Sodium: <120 mEq/L.

No inferential statistical analyses will be performed for the summaries of laboratory data.

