8.6 VITAL SIGNS AND PULSE OXIMETRY

Vital sign data [systolic blood pressure, diastolic blood pressure, pulse, respiration rate, temperature, mean arterial pressure (MAP)] will be collected at each study time point, and pulse oximetry/FiO₂ data will be collected through Study Day 7. Summaries will be prepared for each time point as well as the changes from baseline (i.e., last observation prior to Randomization). Additional summaries of changes relative to ELAD start date/time will be provided for subjects in the ELAD treatment group. For comparison purposes, changes relative to End of Study Day 2 (± 6 hours) will be summarized for the Control treatment group. Proportion of subjects with MAP <60 mmHg vs. ≥60 mmHg will be presented by study group. No inferential statistical analyses will be performed for the summaries of vital sign data.

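### For subjects with repeat screening values, SAP 4.4 selects baseline by randomization date while SAP 8.5 selects it by date/time, so the two rules can give different baselines for the same laboratory test

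*SAP*

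**What the plan says.** SAP 4.4, which introduces the baseline tables, gives a selection rule with a condition. Where a subject has more than one screening value, "the last record before the randomization date will be used for analysis". The subsections beneath it list the variables to be tabulated. Section 4.4.2 includes the MELD score and its components (creatinine, total bilirubin, INR), and 4.4.4 lists creatinine, INR and mean arterial pressure.

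SAP 8.5 has its own definition for laboratory tests: "The baseline evaluation of a laboratory parameter is defined as the last evaluation of that parameter prior to randomization date/time". SAP 7.3.6, which models MELD, total bilirubin, creatinine, INR and sodium, states: "All changes will be calculated relative to randomization date/time". SAP 8.6 takes the vital-sign baseline as the last observation before Randomization, treated as an event and not as a calendar day.

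Protocol 5.2.3 describes the screening tests as those "which are used as Baseline values required for subsequent assessments of change in key parameters" and adds that "these tests and assessments must be performed within 24 hours prior to randomization".

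**The concern.** A 24-hour look-back from randomization normally covers part of the randomization day and part of the day before. A rule that stops at the calendar date cannot use the part of the window closest to randomization. A rule that stops at the date and time can. Where a subject was tested on an earlier day and again on the day of randomization, 4.4 and 8.5 therefore select different records for the same test.

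The stake is the consistency of the baseline data. The subject's baseline MELD in the 4.4 table could differ from the one behind the change-from-baseline tables. It could also predate the protocol's own window, so that the baseline table shows a value beyond an entry limit for a subject who was eligible on the later draw. SAP 7.1.2 splits overall survival (OS) by baseline MELD, bilirubin, creatinine and INR, and 7.1.3 uses baseline MELD, bilirubin and creatinine as candidate Cox covariates. Neither section says which definition of baseline it takes.

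**Working it through.** The plan states no figure on this point, so the check compares the rules.

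**The rules side by side**

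| Section | Cut-off for baseline | Pre-randomization repeat drawn the same day |
|---|---|---|
| SAP 4.4 (only if more than one screening value) | randomization date | passed over |
| SAP 8.5, laboratory | randomization date/time | kept |
| SAP 7.3.6, changes in MELD and labs | relative to randomization date/time | consistent with keeping it |
| SAP 8.6, vital signs | Randomization (event) | kept |
| Protocol 5.2.3 | within 24 hours before randomization | inside the window |

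SAP 4.4 is the odd one out.

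**Constructed cases, randomization at 14:00 on day 1**

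- One value, day 1 at 08:00. The condition in 4.4 is not met, so the value is used. Both rules agree.
- Values on day 0 at 07:00 and day 1 at 08:00. SAP 8.5 takes the second, which is 14 − 8 = 6 hours old. SAP 4.4 takes the first, which is (24 − 7) + 14 = 31 hours old and outside the 24-hour window.
- Values on day 1 at 06:00 and 11:00. SAP 8.5 takes the second, which is 3 hours old. SAP 4.4 read literally finds no record, and 4.4 has no general fallback for that.

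**Do the documents expect repeats?** Yes, in several places:

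- Protocol Table 1, note 8: screening evaluations are repeated if randomization does not follow within 24 hours.
- Protocol 5.2.4: redrawing one MELD component outside the 6-hour span means redrawing all three.
- Protocol 5.2: a subject who did not qualify may be considered again.
- Exclusion criterion 8: bilirubin is compared over the previous 72 hours, which needs more than one value.

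Under note 8, the earlier value is by construction older than the protocol's window. The documents do not say how many repeats will be stored as screening records, or how many will fall on different dates.

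**Illustration only.** Assume a subject has exactly two values, independent and uniform over the 24 hours before randomization at clock hour h. None of this is in the documents. With p = h/24:

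- the rules pick different values with probability 2p(1 − p);
- both values are same-day, so 4.4 gives none, with probability p²;
- when the rules differ, the mean gap is (h + 24)/2 − h/2 = 12 hours.

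| h | p | rules differ | 4.4 gives no value |
|---|---|---|---|
| 08:00 | 0.33 | 0.44 | 0.11 |
| 12:00 | 0.50 | 0.50 | 0.25 |
| 16:00 | 0.67 | 0.44 | 0.44 |
| 20:00 | 0.83 | 0.28 | 0.69 |

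These are proportions of subjects who have two such values, not of the trial.

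**Primary analysis.** The log-rank test in SAP 7.1.1 uses treatment group and survival time only. The power statements in SAP 1.3 depend on events, hazard ratio and alpha: Φ(½√D·|ln HR| − 1.96) gives 0.900 for 55 events at 0.417 and 0.901 for 65 events at 0.447, matching the stated 90%. No baseline laboratory value enters either calculation.

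**The case against.** The strongest reply is that this is loose wording. The opening sentence of 4.4 speaks of demographics, screening vital signs and medical history, not laboratory tests. SAP 8.5 is specific to laboratory parameters, and a specific definition can be read as overriding a general one. The literal rule also gives an absurd result when all repeats are same-day, which suggests that the authors simply meant before randomization. The Child-Pugh notes within 4.4 use that very expression.

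This shows that the intent was probably benign. It does not remove the conflict. MELD, creatinine, bilirubin and INR are listed under 4.4, so its rule can be read as covering them. The SAP does distinguish date from date/time elsewhere: 8.1 has a separate rule for a missing time on the randomization date, and 8.3 defines treatment-emergent events by date/time. A programmer working from 4.4 could reasonably code a date comparison.

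Three stronger readings are tempting, and the documents do not support them:

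- A reader might infer that 4.4 discards same-day screening values in general. It does not, because the rule applies only when more than one value is recorded.
- A reader might take the share of the 24-hour window falling on the randomization date (h/24, for example 33% at 08:00) as the share of subjects affected. It measures a time window under an assumed uniform spread. The relevant count is subjects with repeats, and it is not given.
- A reader might conclude that the OS subgroups and Cox models will use the older values. SAP 7.1.2 and 7.1.3 cite no baseline rule, so that is possible but not established. The former are called descriptive and the latter exploratory.

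Nor does the rule touch enrolment, since eligibility is reviewed before randomization (Protocol 5.3.2). All the values concerned precede assignment, so it gives no systematic advantage to either arm.

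**Conclusion.** The point holds as a minor inconsistency. For subjects with more than one screening value, the literal 4.4 rule and the 8.5 rule can return different baselines. The 4.4 value may be older than the protocol's window allows, or absent.

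This rests on two conditions: that 4.4 is applied as written to the laboratory variables listed under it, and that earlier and repeat values are both held as screening records. The direct effect is on the 4.4 baseline tables and their agreement with 8.5. An effect on 7.1.2 and 7.1.3 is an open question because those sections do not name their source. The size cannot be stated from the documents.

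**What to change.** In SAP 4.4, replace "the last record before the randomization date will be used for analysis" with a rule that takes the last non-missing record prior to the randomization date/time. State there that this single definition of baseline also applies in 7.1.2, 7.1.3, 7.3.6, 8.5 and 8.6. Leave unchanged the places where the SAP deliberately uses another reference point: the start value for early bilirubin change (7.2.2), the Lille score (7.3.5), and the additional summaries relative to ELAD start or End of Study Day 2.

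The cost is one phrase and a cross-reference. The definition already in 8.5 depends on draw times, so no new data are needed.
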